8.3.7 Guidelines for reporting product complaints

Any defect in the IMP must be reported as soon as possible by the Investigator to the monitoring team that will complete a product complaint form within required timelines.

Appropriate information (eg, samples, labels or documents like pictures or photocopies) related to product identification and to the potential deficiencies may need to be gathered. The Investigator will assess whether or not the quality issue has to be reported together with an AE or SAE.

8.4 TREATMENT OF OVERDOSE

The Sponsor does not recommend specific treatment for an overdose (defined in [Section 8.3.6](#)).

In the event of an overdose, the Investigator should:

1. Contact the Medical Monitor immediately.
2. Closely monitor the participant for any AE/SAE and laboratory abnormalities until SAR442720 can no longer be detected systemically (at least 5 days).
3. Obtain a plasma sample for PK analysis within 1 to 2 days from the date of the last dose of study intervention if requested by the Medical Monitor (determined on a case-by-case basis).
4. Document appropriately in the CRF.

Decisions regarding dose interruptions or modifications will be made by the Investigator in consultation with the Medical Monitor based on the clinical evaluation of the participant.

8.5 PHARMACOKINETICS

Plasma samples will be obtained for PK analysis of SAR442720 as outlined in the SoA (see [Section 1.3](#)). Concentrations at each time point will be reported.

- Whole blood samples of approximately 1.5 mL will be collected and processed into plasma for measurement of plasma concentrations of SAR442720 as specified in the SoA (see [Section 1.3](#)). Instructions for the collection and handling of biological samples will be provided by the sponsor. The actual date and time (24-hour clock time) of each sample will be recorded.
- Samples collected for analyses of SAR442720 plasma concentration may also be used for exploratory analysis, such as metabolic profiling of SAR442720.

Serum samples will be obtained for PK analysis of pembrolizumab as outlined in the SoA (see [Section 1.3](#)). Concentrations at each time point will be reported.

- Whole blood samples of approximately 1.5 mL will be collected and processed into serum for measurement of serum concentrations of pembrolizumab as specified in the SoA (see [Section 1.3](#)). Instructions for the collection and handling of biological samples will be provided by the sponsor. The actual date and time of each sample will be recorded. Pharmacokinetic samples will be tested by the Sponsor or Sponsor's designee.
- Samples collected for analyses of pembrolizumab serum concentration may also be used for other analysis, such as immunogenicity assessment.
- Plasma samples will be obtained for PK analysis of adagrasib as outlined in the SoA (see [Section 1.3](#)). Concentrations at each time point will be reported.
- Whole blood samples of approximately 1.5 mL will be collected and processed into plasma for measurement of plasma concentrations of adagrasib as specified in the SoA (see [Section 1.3](#)). Instructions for the collection and handling of biological samples will be provided by the Sponsor. The actual date and time of each sample will be recorded.
- For Part-3A and Part-4, the PK parameters of SAR442720 and adagrasib will be calculated using a non-compartmental method. The PK parameters (eg, C_{max} , time to achieve maximum concentration [T_{max}], area under the concentration–time curve from Time 0 to Time t [AUC_{0-t}], area under the concentration–time curve from Time 0 to infinity [AUC_{inf}], elimination half-life [$t_{1/2}$], if possible, and the accumulation ratio) of SAR442720 and adagrasib will be assessed for each evaluable participant.
- PK population analysis may be conducted to obtain the PK parameters of SAR442720, pembrolizumab, and/or adagrasib. If performed, the results will be summarized in a separate report.
- Samples collected for analyses of the concentration of SAR442720, pembrolizumab, and adagrasib may also be used to evaluate safety or efficacy aspects related to concerns arising during or after the study.

8.6 PHARMACODYNAMICS

Whole blood samples will be collected throughout the study as outlined in the SoA ([Section 1.3](#)). RNA expression signatures for RAS-MAPK pathway and other relevant genes will be used to explore target engagement and pharmacodynamic (PDy) modulation in Part1 and Part2.

In Part-1, fresh tumor tissue is required for PDy biomarker analyses unless the investigator determines that the tumor site is not amenable to biopsy and poses a significant risk to participant safety. The Sponsor will evaluate this requirement on a case-by-case basis (see [Section 1.3 Table 2](#)). An EOT biopsy will be requested and is optional. Biopsies will be collected 1) prior to treatment; 2) on treatment; and 3) optional at EOT or disease progression.

In Part-2 and Part-3, baseline tumor tissue is required, on-treatment and EOT biopsy is optional ([Table 3](#) and [Table 4](#)).

The primary purpose of the on-treatment biopsies is to assess for target inhibition by quantifying expression patterns of genes downstream of the RAS-MAPK, key immune pathways and mutational landscape. Where sufficient tumor tissue passing quality control is available, predictive biomarkers will be explored. Details on processes for collection and shipment can be found in the laboratory manual.

8.7 GENETICS

Eligible mutations will be based on prior genotyping results using a clinically validated or qualified test. This test may have been performed on either tumor tissue or ctDNA samples. Sites must provide the Sponsor with the report. Where available, archival tumor tissue will be collected for retrospective central lab testing. Where a discrepancy lies between the local and central results for the eligibility defining mutation, the participant will remain on study. For data analysis purposes, results from the central laboratory will supersede those of the local laboratory.

Fresh tumor biopsy is collected, where sufficient tissue passing QC is available, with the aim of confirming mutations identified on the genomic report provided at enrollment, assessing RAS-MAPK pathway and other gene expression patterns as a measurement of drug activity. In addition, we will use genomic data from tumor tissue to 1) define biomarkers for sensitivity, resistance, and toxicity to SAR442720 and other agents in combination and 2) to assess clonal dynamics and RNA expression changes within the tumor cell population before, during and after treatment. Blood sample at baseline will be used as germline control from consenting participants in Part-2.

See Appendix 5 ([Section 10.5](#)) for information regarding genetic research. Details on processes for collection and shipment and destruction of these samples can be found in the laboratory manual.

Genetic analyses will not be performed on PK samples. Participant confidentiality will be maintained. Any changes in the timing or addition of time points for any planned study assessments must be documented and approved by the relevant study team member and then archived in the Sponsor and site study files but will not constitute a protocol amendment. The IRB will be informed of any safety issues that require alteration of the safety-monitoring scheme or amendment of the ICF.

8.8 BIOMARKERS

Blood samples will be collected as outlined in the SoA ([Section 1.3](#)) for RNA expression analysis for evaluation of RAS-MAPK gene signature and other gene expression patterns in Part-1 and Part-2 participants. The aim of this is to assess the effects of the drugs on global gene regulation.

Blood samples will be collected as outlined in the SoA ([Section 1.3](#)) for immune-phenotyping analysis to evaluate modulation of key immune cells in peripheral blood in Part-1 and Part-2.

Blood samples will be collected as outlined in the SoA ([Section 1.3](#)) for ctDNA analysis to assess temporal clonal dynamics in tumors.

Blood samples will be collected as outlines in the SoA ([Section 1.3](#)) for measurement of cytokine/soluble factors that are known to be modulated by RAS-MAPK pathway and/or may reflect changes in the immune system after exposure to SHP2 or PD-1 blockade in Part-1 and Part-2.

Special procedures for collection, handling, storage and shipment of samples for biomarker analysis will be described in a separate laboratory manual which will be available at the investigational site. Samples may be stored for a maximum of 15 years (or according to local regulations) following the last participant's last visit for the study at a facility selected by the Sponsor to enable further analysis of biomarkers related to SAR442720 and/or cancer or related diseases, or to develop methods, assays, prognostics and/or companion diagnostics, and potentially to identify new drug targets or biomarkers.

Details of sample collection, processing and logistics are described in the laboratory manual.

8.9 IMMUNOGENICITY ASSESSMENTS

Immunogenicity of pembrolizumab will not be assessed, given the fact that the incidence of anti-drug antibody (including neutralizing antibody) positivity is not comparable across studies and assays, due to several factors, including but not limited to differences in assay methodology, sample handling, timing of sample collection, concomitant medications, and underlying disease. Participants with positive treatment-emergent anti-pembrolizumab antibody is approximately 2% (0.5% positive neutralizing antibody) according to US Package Insert, and there was no evidence of an altered PK profile or increased infusion reactions in these participants. In addition, pembrolizumab showed flat exposure-response profile in terms of safety across a dose range of 1 to 10 mg/kg, and it is unlikely for SAR442720 to trigger additional safety concerns of pembrolizumab, due to altered immunogenicity.

As SAR442720 and adagrasib are small molecules, immunogenicity testing of SAR442720 or adagrasib is not required.

8.10 HEALTH ECONOMICS OR MEDICAL RESOURCE UTILIZATION AND HEALTH ECONOMICS

Not applicable.

8.11 USE OF BIOLOGICAL SAMPLES AND DATA FOR FUTURE RESEARCH

Future research may help further the understanding of disease subtypes, disease biology, related conditions, drug response and toxicity, and can help identify new drug targets or biomarkers that predict participant response to treatment. Therefore, data and biological samples will be stored and used for future research when consented to by participants unless prohibited by local laws or IRBs/IECs (in such case, consent for future use of sample will not be included in the local ICF).

For participants who consent to the storage and use of their data and remaining and/or extra clinical samples, data and samples may be used after the study ends for future research related either to the drug, the mechanism of action, and the disease or its associated conditions. Such research may include, but is not limited to, performing assessments on DNA, RNA, proteins or metabolites. If future research on genetic material is performed, this will also be limited to the purpose of addressing research questions related to the drug, the mechanism of action, the disease or its associated conditions.

In the event future research is conducted for other purposes, the study participants will be informed of those purposes and will be given means to object to those research projects.

Data and samples will be used in compliance with the information provided to participants in the ICF Part-2 (future research).

All study participant data and samples will be coded such that no participant direct identifiers will be linked to them. Coded data and samples may be transferred to a Sponsor site (or a subcontractor site), which may be located outside of the country where the study is conducted. The Sponsor adopts safeguards for protecting participant confidentiality and personal data (see [Section 10.7](#)).

The samples will be stored for a maximum of 15 years after the end of the study. Any samples remaining at the end of retention period will be destroyed. If a participant requests destruction of his/her samples before the end of the retention period, the Investigator must notify the Sponsor (or its contract organization) in writing. In such case, samples will be destroyed and related coded data will be anonymized unless otherwise required by applicable laws.

Study participant coded data will be stored for future research for up to 25 years after the end of the study. If data are still considered of important scientific value after this period, coded data already available will be anonymized unless otherwise required by applicable laws (the same will apply to the data of a study participant who has requested the destruction of his/her samples).

Participant's coded data sets provided to researchers for a specific research project will be available to the researchers for a maximum of 2 years after the end of their specific project (end of project is defined by publication of the results or finalization of the future research project report).

9 STATISTICAL CONSIDERATIONS

9.1 STATISTICAL HYPOTHESES

The primary objective of Part-1 is to find the MTD and RP2D for the combination therapy of SAR442720 and pembrolizumab. In Part-2 the study is designed to assess clinical benefit of SAR442720 when combined with pembrolizumab. Similarly, Part-3 is designed to find the RP2D, explore the anti-tumor activity, and PK of SAR442720 in combination with adagrasib. Part-4 is to evaluate the effect of food and relative bioavailability of different formulations. Therefore, there is no formal statistical hypothesis and testing procedure defined in this study.

9.2 SAMPLE SIZE DETERMINATION

The sample size is not calculated from statistical consideration since there will not be any formal statistical test performed. Overall, up to 134 participants will be enrolled.

In Part-1, at least 6 participants need to be treated at the MTD. After MTD is identified, another 6 participants will be treated at the MTD to confirm the decision and determine the RP2D. Therefore, a range of 18 to 24 DLT-evaluable (defined in [Section 9.3](#)) participants will be enrolled in the Part-1 of this study. The actual sample size will vary depending on DLTs observed and the number of dose levels explored.

In Part-2, 40 participants, including 20 participants in Cohort A1 with PD-L1 TPS $\geq 50\%$ and 20 participants in Cohort A2 with PD-L1 TPS in 1-49%, will be enrolled at the RP2D identified from Part-1. [Table 18](#) lists estimated ORR and the corresponding 90% exact CIs by number of responders in Part-2.

Table 18 - Estimated objective response rate (ORR) and 90% CI in Part-2

Number of responders (N=20)	ORR	90% CI for ORR (Clopper-Pearson)
4	20%	(7.1%, 40.1%)
5	25%	(10.4%, 45.6%)
6	30%	(14.0%, 50.8%)
7	35%	(17.7%, 55.8%)
9	45%	(25.9%, 65.3%)
11	55%	(34.7%, 74.1%)
12	60%	(39.4%, 78.3%)

With a sample size of 20 study participants in each cohort of Part-2, the probability of observing 1 or more instances of a specific AE with a true incidence rate of 1%, 2%, or 5% is 18.2%, 33.2%, or 64.2%, respectively.

In Part-3A, a range of approximately 15 to 30 DLT-evaluable (defined in [Section 9.3](#)) participants will be enrolled in this study. The actual sample size will vary depending on DLTs observed and the number of dose levels explored.

In Part-3B, approximately 40 participants will be enrolled at the RP2D identified from Part-3A. [Table 19](#) lists the estimated ORR and the corresponding 90% exact CIs by the number of responders in Part-3B.

Table 19 - Estimated objective response rate (ORR) and 90% CI in Part-3B

Number of responders (N=40)	ORR	90% CI for ORR (Clopper-Pearson)
13	32.5%	(20.4%, 46.6%)
15	37.5%	(24.7%, 51.7%)
17	42.5%	(29.2%, 56.7%)
19	47.5%	(33.8%, 61.5%)
21	52.5%	(38.5%, 66.2%)
23	57.5%	(43.3%, 70.8%)
24	60.0%	(45.8%, 73.1%)

With a sample size of 40 study participants in Part-3B, the probability of observing 1 or more instances of a specific AE with a true incidence rate of 1%, 2%, or 5% is 33.1%, 55.4%, or 87.1%, respectively.

In Part-4, up to approximately 12 participants are expected to be enrolled. By assuming intra-subject variability of the steady-state AUC is [REDACTED], 12 participants will achieve a maximum imprecision of [REDACTED]. When 9 participants are PK evaluable, the maximum imprecision will be approximately [REDACTED].

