SAR442720 and pembrolizumab will be administered on a continuous basis, with SAR442720 administered orally at the RP2D determined from Part-1, and pembrolizumab administered intravenously at 200 mg Q3W or 400 mg Q6W. The SAR442720 tablet formulation (test) will be administered during the first cycle (21 days), and starting from C2D1, SAR442720 capsule formulation (reference) will be administered until the end of treatment (EOT). On C1D1, each participant will receive SAR442720 tablet in combination with pembrolizumab with a moderate-calorie moderate-fat breakfast after an overnight fast of 10 hours. The breakfast should be consumed within 0.5 hour, and there should be another 4 hour fast after the completion of breakfast. On C1D15, each participant will receive SAR442720 tablet after a 10 hour overnight fast prior to dosing on C1D15, followed by a 4 hour fast postdose. On C2D1, each participant will receive SAR442720 capsule in combination with pembrolizumab after a 10 hour overnight fast prior to dosing on C2D1, followed by a 4 hour fast postdose. For all other days (except for C1D1, C1D15, and C2D1), participants will be fasted for 1 hour prior and 1 hour after each SAR442720 dose. Water will be permitted ad lib for participants in either fasted or fed state, except for 1 hour before and 1 hour after the administration of SAR442720. Participants will be instructed to take SAR442720 with 240 mL of water.

Disclosure Statement: This is a non-randomized study with SAR442720 in combination with other agents (pembrolizumab or adagrasib) with no masking in participants with advanced malignancies.

Number of participants:

Approximately 18 to 24 DLT evaluable participants are expected to be enrolled during the Dose Escalation and mini-expansion cohort (Part-1). It assumes 3 combination dose levels (as shown above) with 3 to 6 participants per dose level. At least 6 participants need to be treated at the MTD. After the MTD is identified, another 6 participants will be treated at the MTD to confirm the decision and determine the RP2D. The actual sample size will vary depending on DLTs observed and the number of dose levels explored.

In Part-2 approximately 40 participants will be enrolled and treated at RP2D determined from Part-1. It is planned to enroll 20 participants with PD-L1 TPS $\geq 50\%$ (Cohort A1) and 20 participants with PD-L1 TPS in 1-49% (Cohort A2).

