4.1.2 Dose escalation

In Part-1 and Part-3A, dose escalation will follow mTPI2 design with a minimum of 3 participants evaluable for DLT in the first cycle. A participant will be considered evaluable for DLT assessment if he/she receives at least 4 out of the 6 planned doses of SAR442720 in the first cycle and completes the DLT observation period or if he/she experiences a DLT in the DLT observation period. A participant who is not DLT-evaluable will be replaced to achieve a minimum of 3 DLT-evaluable participants at the same cohort.

The actual dose selected at each dose escalation decision, and the MTD identified at the conclusion of the dose escalation phase, will be determined by the Study Committee, in agreement with the Sponsor's Study Medical Manager, which may select a dose at or below the model's recommendation and should not select a dose that is suggested to be over toxic by the model. The Study Committee will review the overall safety of all dose levels. More details in the model and its operating characteristics can be found in Appendix 11 ([Section 10.11](#)).

The adaptive dose escalation design is based on the boundaries generated from the mTPI2 design. The dose escalation will stop if the next recommended dose has been collectively evaluated in at least 2 previous escalation cohorts.

It is anticipated that in Part-1 12 to 18 DLT-evaluable participants and in Part-3A 15 to 30 DLT-evaluable participants will be enrolled in the dose escalation. The actual total number of participants required will depend on the number of dose levels evaluated and on the incidence and timing of observed DLTs.

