Part-3B aims to determine the anti-tumor activity of SAR442720 in combination with adagrasib in participants with NSCLC and KARAS G12C mutations, which can result in an increased ORR. The goal of the combination therapy approach is to expand the spectrum of patients who respond to targeted KRAS G12C therapy and to improve the quality of clinical responses (ie, durable response and prolonged PFS) beyond what can be achieved with monotherapy alone.

The design of the study is a non-randomized study in which the experimental combination will be assessed in a single cohort for each indication. The ORR will be assessed using RECIST v1.1. The objective response will be assessed by the Investigator in first intention. Central imaging reading may be done retrospectively if significant activity is observed.

Part-4 aims to assess the impact of formulation and preliminary impact of food on the PK of SAR442720 in combination with pembrolizumab. Part-4 is an open label, non-randomized fixed-sequence study, intending to assess preliminary effect of food on SAR442720 tablet and relative bioavailability of SAR442720 tablets versus capsules in participants with advanced malignancies. The PK of SAR442720 under fasted state will be served as the test treatment of formulation bridging; therefore, both the food effect and formulation effect can be assessed in the same participants, to reduce the number of participants needed.

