#### Part-3

Part-3 of this open-label, multi-center, un-controlled, non-randomized study, will assess the safety, RP2D, anti-tumor activity, and PK of SAR442720 in combination with adagrasib in participants with NSCLC harboring KRAS G12C mutation.

Part-3A of the study will investigate the safety and tolerability of SAR442720 in combination with adagrasib and confirm RP2D. There are 6 dose levels in consideration: the starting dose (dose level 1 [DL1]) of IMP combination will be 100 mg BIW and 400 mg BID for SAR442720 and adagrasib respectively, dose level 2 (DL2) will be 140 mg BIW and 400 mg BID, dose level 3a (DL3a) will be 140 mg BIW and 600 mg BID, dose level 3b (DL3b) will be 200 mg BIW and 400 mg BID, dose level 4 (DL4) will be 200 mg BIW and 600 mg BID, and dose level (-1) ([DL-1]) will be 80 mg BIW and 400 BID. A minimum of 3 DLT evaluable participants for each dose level is required. The DLT observation period is 1 cycle (21 days). The Study Committee will review the overall safety, PK/PD, and clinical activity data and in agreement with the Sponsor's Study Medical Manager, will decide the recommended dose for the expansion phase.

Part-3B dose expansion will assess the anti-tumor activity and safety of SAR442720 combined with adagrasib in participant with NSCLC harboring KRAS G12C mutation. This study will start once RP2D for SAR442720 and adagrasib from Part-3A dose escalation is confirmed. Approximately 40 participants will be enrolled.

Part-4 of this study will assess the effect of food on PK of SAR442720 tablet, when dosed in combination with pembrolizumab in participants with advanced malignancies. It will also evaluate the relative bioavailability of SAR442720 tablet formulation (test) compared to the capsule formulation (reference) when dosed in combination with pembrolizumab. Approximately 12 participants are expected to be enrolled.

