## 2 SAMPLE SIZE DETERMINATION

The sample size is not calculated from statistical consideration since there will not be any formal statistical test performed. Overall, up to 134 participants will be enrolled.

In Part-1, at least 6 patients need to be treated at the MTD. After MTD is identified, another 6 patients will be treated at the MTD to confirm the decision and determine the RP2D. Therefore, a range of 18-24 DLT-evaluable (defined in [Section 3](#)) patients will be enrolled in the Part-1 of this study. The actual sample size will vary depending on DLTs observed and the number of dose levels explored.

In Part-2, 40 participants, including 20 patients in Cohort A1 with PD-L1 TPS $\geq$ 50% and 20 patients in Cohort A2 with PD-L1 TPS in 1-49%, will be enrolled at the RP2D identified from the Part-1. With a sample size of 20 study participants in each cohort of Part-2, the probability of observing 1 or more instances of a specific AE with a true incidence rate of 1%, 2%, or 5% is 18.2%, 33.2%, or 64.2%, respectively.

Part-3A, a range of 15 to 30 DLT-evaluable participants will be enrolled in this study. The actual sample size will vary depending on DLTs observed and the number of dose levels explored.

Part-3B, 40 participants will be enrolled at the RP2D identified from the Part-3A. With a sample size of 40 study participants in each cohort of Part-3B, the probability of observing 1 or more instances of a specific AE with a true incidence rate of 1%, 2%, or 5% is 33.1%, 55.4%, or 87.1%, respectively.

Part 4, 12 participants are expected to be enrolled in each group. By assuming AUC single dose Coefficient of Variation is [REDACTED], 12 participants in each group will achieve a maximum imprecision of [REDACTED]. When the AUC ratio is [REDACTED], the 90% CI would be [REDACTED] [REDACTED] respectively. When 9 participants are PK evaluable in each group, the maximum imprecision would be [REDACTED]. When the AUC ratio is [REDACTED], the 90% CI would be [REDACTED] [REDACTED] respectively.

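### The overall maximum of 134 participants leaves out Part-4; the stated part maxima sum to about 146

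*Protocol*

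**What the plan says.** Protocol Section 9.2 states, without qualification: "Overall, up to 134 participants will be enrolled". SAP Section 2 repeats the sentence.

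The same protocol section then sizes each part. Part-1 has "a range of 18 to 24 DLT-evaluable" participants, Part-2 has 40 (20 per cohort), Part-3A has about 15 to 30 DLT-evaluable participants, and Part-3B has about 40. The section ends with the fifth component: "In Part-4, up to approximately 12 participants are expected to be enrolled". The synopsis and Section 4.1 also give about 12 for Part-4.

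The SAP describes Part-4 in two ways. Section 1.1 says "Approximately 12 participants are expected to be enrolled" and mentions no groups. Section 2 says "12 participants are expected to be enrolled in each group" and uses the per-group wording twice more in its precision statement. Protocol Section 4.2 describes an open-label, fixed-sequence design in which "both the food effect and formulation effect can be assessed in the same participants, to reduce the number of participants needed".

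**The concern.** A figure introduced as an overall maximum should be at least the sum of the part maxima. Here it equals that sum with one part missing. Part-4 is one of the study's four parts, has its own primary objectives, and is sized in the same section as the total. Parts 3 and 4 entered with the same amendment, and the total counts one but not the other.

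At stake is whether the stated size of the study is right. As written, a sponsor could stay within every part limit and still exceed the overall limit. A reader of the SAP also cannot tell whether Part-4 means 12 people or 12 in each of several groups.

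**Working it through.** **Inputs (Protocol Section 9.2, repeated in SAP Section 2 except where noted above for Part-4)**

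| Part | Low | High |
|---|---|---|
| 1 | 18 | 24 |
| 2 | 40 | 40 |
| 3A | 15 | 30 |
| 3B | 40 | 40 |
| 4 | – | 12 |

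The Part-1 range includes the 6-participant mini-expansion. Protocol Section 4.1.2 gives 12 to 18 for escalation alone; 12 + 6 = 18 and 18 + 6 = 24.

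**Step 1. Reproduce the stated total.**
24 + 40 + 30 + 40 = 134. This is an exact match without Part-4.

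**Step 2. Add Part-4.**
134 + 12 = 146. The difference is 12, and 12 / 134 = 9.0%.

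**Step 3. Look for a reading of 134 that includes Part-4.**

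- Part-1 at its escalation-only maximum: 18 + 40 + 30 + 40 + 12 = 140.
- Part-4 at the 9 PK-evaluable participants mentioned in Section 9.2: 24 + 40 + 30 + 40 + 9 = 143.
- The only exact match found with 12 in Part-4 is 12 + 40 + 30 + 40 + 12 = 134. It pairs the escalation-only minimum of Part-1 with the maximum of Part-3A, which does not give an upper limit.

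**Step 4. When would 134 be passed?**
With Parts 2 and 3B at 40 each and Part-4 at 12, the room left for Part-1 plus Part-3A is 134 − 40 − 40 − 12 = 42. Their stated combined range runs from 18 + 15 = 33 to 24 + 30 = 54, so the threshold lies inside it.

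- Part-1 at 18: passed if Part-3A exceeds 42 − 18 = 24.
- Part-1 at 24: passed if Part-3A exceeds 42 − 24 = 18.

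**Step 5. The Part-4 count in the SAP.**
Taken literally, 12 per group with two groups (an assumption, since the number of groups is not given) would mean 24 in Part-4 and 134 + 24 = 158 overall. That conflicts with SAP Section 1.1 and with the single cohort in Protocol Section 4.2.

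**The case against.** The strongest reply is that 146 is no firmer a ceiling than 134. Most part figures are approximate, and the documents say that the Part-1 and Part-3A sizes will vary with the DLTs seen and the dose levels explored. The Part-3A maximum of 30 rests on five dose levels of up to 6, yet Table 14 of the protocol has six rows and SAP Section 1.1 counts six levels. At 6 per level that is 36, and the sum becomes 24 + 40 + 36 + 40 + 12 = 152. Both escalation figures also count DLT-evaluable people, while Protocol Section 4.1.2 says "A participant who is not DLT-evaluable will be replaced to achieve a minimum of 3 DLT-evaluable participants at the same cohort", so enrolment can run higher. All of this stands, but each point pushes the ceiling up and none rescues 134.

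A second reply is that the gap of 12 is the upper case. Protocol Section 2.3.1.1 reports 17 participants exposed in this study by 17 July 2021, without a split by part. If Part-1 had closed at 17, the sum would be 17 + 40 + 30 + 40 + 12 = 139, still above 134.

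A third is that the SAP's per-group wording may only mean per condition, since each participant contributes to every condition. That is possible, but people are not enrolled per condition, so the sentence still needs correcting. It is fair to add that the wording sits inside a precision statement whose figures are blacked out. The SAP there assumes a single-dose coefficient of variation, whereas Protocol Section 9.2 assumes intra-subject variability of the steady-state AUC. Whether the SAP figures were computed for separate groups cannot be seen.

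**Conclusion.** The concern holds and is minor. The overall maximum in both documents omits Part-4 and is about 12 too low (134 against about 146, or 9%). The 146 is the sum of the stated upper figures, on the assumption that Part-4 participants are additional to those in the other parts; no passage says otherwise. It is not a forecast of enrolment and could itself be exceeded through replacement or added dose levels.

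None of the per-part sizes, the response-rate intervals in Tables 18 and 19 of the protocol, or the adverse-event detection probabilities depends on the total. The SAP's Part-4 count is inconsistent with its own Section 1.1 and with Protocol Section 4.2, and should be settled at the same time.

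**What to change.** In Protocol Section 9.2 and SAP Section 2, replace the sentence giving the total with, for example:

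> The upper figures for the five components sum to approximately 146 (24 + 40 + 30 + 40 + 12). The Part-1 and Part-3A figures count DLT-evaluable participants, so the number enrolled may be higher where participants are replaced under Protocol Section 4.1.2.

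If 134 was meant to exclude Part-4, say so instead. While editing, confirm that the Part-3A maximum of 30 fits the number of dose levels listed.

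In SAP Section 2, change the three per-group phrases for Part-4 to describe one cohort of about 12 (9 PK-evaluable), each measured under all conditions. Confirm that the blacked-out precision figures were computed for that within-participant design.

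The cost is one sentence in each document and three phrases in the SAP. Correcting the total changes no analysis. The Part-4 precision figures would need recomputing only if they turn out to assume separate groups.
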